#### 7.8.1 Adverse events

AEs will be coded with the most recent version of MedDRA.

The analyses of AEs will be descriptive in nature. All analyses of AEs will be based on the number of patients with AEs and not on the number of AEs. System organ classes (if applicable) will be sorted according to the standard sort order specified by the EMA, preferred terms (if applicable) will be sorted by total frequency (within system organ class).

For further details on summarization of AE data, please refer to "Handling and summarization of adverse event data for clinical trial reports and integrated summaries" ([4](#)) [*KM Asset BI-KMED-BDS-HTG-0041*] and "Handling of missing and incomplete AE dates" ([3](#)) [*KM Asset BI-KMED-BDS-HTG-0035*].

The analysis of AEs will be based on the concept of treatment emergent AEs. This means that all AEs will be assigned to the screening phase, re-induction on-treatment period (i.e. re-induction treatment phase plus REP), maintenance on-treatment period (i.e. maintenance treatment phase plus REP) or off-treatment period (i.e. follow-up) as defined in [Section 6.1](#). Adverse events occurring in the maintenance and re-induction periods will be separately described. Since only the start date of an AE is collected (without start time), any AE occurrence on the same day as the first re-induction or first maintenance spesolimab administration will be assigned to the respective on-treatment period. For patients who switch directly to maintenance treatment at week 12 of the re-induction period, adverse events occurring on this first day of maintenance treatment will be included in summaries of the maintenance period only. Exposure-adjusted adverse event incidence rates (per the primary endpoint) will be calculated using the following approach:

- 1) The exposure adjusted incidence rate (per 100 subject years) of a selected treatment emergent adverse event is defined as the number of subjects experiencing the adverse event per treatment group during time at risk divided by the total time of subjects at risk in that treatment group to contribute the event to the analysis multiplied by 100 (per 100 subject years), where:
  - 2) Time at risk [subject years] = (date of onset of AE – study drug start date + 1) / 365.25

For safety analysis on the post-flare treatment periods: Time at risk [subject years] = (date of onset of AE – first i.v. disease flare treatment start date + 1) / 365.25

For safety analysis on the disease flare treatment period: Time at risk [subject years] = (date of onset of AE – prior i.v. disease flare treatment start date + 1) / 365.25

- 3) If, for a subject, the selected treatment emergent adverse event didn't occur then the time at risk will be censored at min (date of death, date of end of applicable treatment period per [Section 6.1](#), or date of cut-off if interim analysis performed). For each selected treatment emergent AE, the exposure adjusted incidence rate will be calculated as:
- 4) Incidence rate [1/100 Subject years (pt-yrs)] = 100 \* number of subjects with TEAE / Total TEAE-specific time at risk [subject years].

An overall summary of AEs will be presented. This overall summary will include summary statistics for the class of other significant AEs derived according to an adaptation of the ICH E3 ([6](#)) and for the class of AESIs.

The following are considered as AESIs (cf. CTP section 5.2.6.1):

- Infusion reactions including anaphylactic reaction
- Severe infections (according to RCTC grading)
- Opportunistic and mycobacterium tuberculosis infections
- Hepatic injury

*A hepatic injury is defined by the following alterations of hepatic laboratory parameters:*

- a. ALT or AST >5x ULN*
- b. ALT or AST >3x ULN with the appearance of fatigue, nausea, vomiting, right upper quadrant pain or tenderness, fever, rash, and/or eosinophilia (> 5%)*
- c. AST and/or ALT ≥3 fold ULN combined with an elevation of total bilirubin ≥2 fold ULN measured in the same blood draw sample*

The investigator identified AESI will be captured from the eCRF and reported in the “Investigator reported AESI” table. In addition, user defined adverse event concepts (UDAEC) identified through specific search criteria will be reported separately ([Table 7.8.1: 1](#)).

Adverse Events classified as ‘other significant’ will be reported using an adaptation of the ICH E3 ([6](#)) and will include those non-serious and non-significant AEs which were reported with ‘action taken = drug withdrawn’ or ‘action taken = reduced’.

The exposure-adjusted incidence rate and frequency of patients with AEs will be summarised by treatment, primary system organ class and preferred term. AEs which were considered by the investigator to be drug related will be summarised separately. Separate tables will also be provided for patients with SAEs, patients with AESIs, patients with AE leading to discontinuation of the trial, patients with other significant AEs and User-defined Adverse Event Concepts (UDAEC) (see [Table 7.8.1: 1](#)). AEs will also be summarized by maximum intensity based on the RCTC measure (see [Section 5.4.1](#)).”

For disclosure of AE data on ClinicalTrials.gov, the frequency of patients with non-serious AEs occurring with an incidence of greater than 5% (in preferred terms) will be summarised by primary system organ class and preferred term. The frequency of patients with SAEs will also be summarised.

For disclosure of AE data in the EudraCT register, the frequency of non-serious AEs with an incidence of greater than 5% (in preferred terms) and the frequency of SAEs will be summarised.

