3.3.4.2 Withdrawal of consent for trial participation

Patients may withdraw their consent for trial participation at any time without the need to justify the decision.

This will, however, mean that no further information may be collected for the purpose of the trial and negative implications for the scientific value may be the consequence. Furthermore, it may mean that further patient follow up on safety cannot occur.

If a patient wants to withdraw consent, the investigator should explain the difference between treatment withdrawal and withdrawal of consent for trial participation and explain the options for continued follow up after withdrawal from trial treatment.

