Rationale for change	Align exposure for safety across projects where BI 655130 is given as rescue
Section to be changed	Section 7.3.4 Safety analyses
Description of change	If, for a subject, no treatment emergent adverse event occurred, then the time at risk will be censored at the minimum of (drug stop date + 112 days; last contact date; or, date of database snapshot if interim analysis performed). Changed to:(date of death; drug stop date + 112 days; start date of disease flare treatment with BI 655130;
Rationale for change	Align exposure for safety across projects where BI 655130 is given as rescue
Section to be changed	Section 7.5 Handling of Missing data

Proprietary confidential information © 2022 Boehringer Ingelheim International GmbH or one or more of its affiliated companies

Description of change	If a patient experiences disease worsening during the re-induction period, or a disease flare during the maintenance period prior to observing the efficacy outcome at a specific visit, then all data subsequent to the intake of such rescue Added:to the intake of such rescue medication
Rationale for change	Mistakenly forgotten word
Section to be changed	Section 7.7 Determination of sample size
Description of change	Approximately 170 patients who meet the entry criteria.... Updated: Approximately 160 patients who meet the entry criteria...
Rationale for change	typo
Section to be changed	Section 8 Informed Consent, Trial Records, Data Protection, Publication Policy and Administrative Structure
Description of change	Removed: The trial will be carried out in accordance with the Medical Devices Directive (93/42/EEC) and the harmonised standards for Medical Devices (ISO 14155, current version).
Rationale for change	Not applicable
Section to be changed	Section 8.5.1 Collection, storage and future use of biological samples and corresponding data
Description of change	Measures are in place to comply with the applicable rules for the collection, biobanking and future use of biological samples and clinical data, in particular Removed:.... for the collection , biobanking and Removed: Sample and data usage has to be in accordance with the separate biobanking informed consent Samples and/or data may be transferred to third parties and other countries as specified in the biobanking ICF
Rationale for change	Not applicable as there will be no biobanking in the trial
Section to be changed	10.7 steriod tapering scheme

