## **Re-Induction Period**

The analysis phase as described below is applicable to both the efficacy and safety analyses of the re-induction period.

Table 6.1: 1 Flow chart of analysis phases for re-induction period

Study analysis phase	Description	Start (included)	End (included)
Screening phase	Screening	Earliest of (Date of informed consent, first screening procedure)	Date/time of start of infusion of first re-induction study drug minus 1 minute
Re-induction treatment phase & Residual effects period	Re-induction on-treatment period	Date/time of start of infusion of first re-induction study drug (Day 1 for re-induction)	Patient does not participate in maintenance treatment period: Date of end of infusion of last re-induction study drug + 112 days at 11:59 pm; Patient participates in maintenance treatment period: Date/time of injection of first maintenance study drug minus 1 minute
Follow-up  phase	Off-treatment period	Patient does not participate in maintenance treatment period: Date of end of infusion of last re-induction study drug + 113 days at 12:00 a.m.	Latest of: i) Date of EOS visit (Week 24 visit); ii) last contact date on End of Study page at 11:59 p.m.

Dates are defined individually per patient. If more than one date is associated with a specific visit, measurements associated with a specific date are assigned to a study analysis phase according to the rules specified in the table. An analysis phase will not extend beyond the start date of the following phase.

 The off-treatment period (i.e. Follow-up phase) only exists if the trial completion date is after the date of end of last infusion + 112 days, and if patient did not continue into the Maintenance period.

 This part applies only to patients entering maintenance period after completing re-induction period; it is expected to occur within the period defined by REP. Note that for safety data, i.e., AE where date and time are collected, an event which occurs on the same day of first dose in the following maintenance period, but prior to the administration are assigned to, and reported as a part of the re-induction period.

Assessments done on the same day as the first re-induction treatment dose will be assigned to a study analysis phase based on assessment via date and time. If time is not collected for a particular assessment, then assignment will be to the screening phase.

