## **Pre-Flare Treatment Period**

The analysis phase as described below is applicable to safety analyses only of the pre-flare treatment period.

Table 6.1: 2 Flow chart of analysis phases for pre-flare treatment period

Study analysis phase	Description	Start (included)	End (included)
Screening  phase	Screening	Earliest of (Date of informed consent, first screening procedure)	Date/time of injection of first maintenance study drug minus 1 minute
Maintenance treatment phase & Residual effects period	Maintenance on-treatment period	Date/time of injection of first maintenance study drug (Day 1 for maintenance)	Without flare treatment: Date of injection of last maintenance study drug + 112 days at 11:59 p.m. With flare treatment: Date/time of infusion of first flare study drug minus 1 minutes
Follow-up  phase	Off-treatment period	Without flare treatment: Date of injection of last maintenance study drug + 113 days at 12:00 a.m.	Latest of: i) Date of EOS visit (Week 352 visit); ii) last contact date on End of Study page at 11:59 p.m.

Dates are defined individually per patient. If more than one date is associated with a specific visit, measurements associated with a specific date are assigned to a study analysis phase according to the rules specified in the table. An analysis phase will not extend beyond the start date of the following phase.

 The off-treatment period (i.e. Follow-up phase) only exists if the trial completion date is after the date of end of last injection + 112 days.

 The screening phase does not exist for re-induction treated patients who subsequently receive maintenance treatment.

 Safety data is censored for reporting following intake of disease flare treatment with spesolimab. Measurements collected with date only on the day of first flare treatment are assigned to the pre-flare treatment period.

Assessments done on the same day as the first maintenance treatment dose will be assigned to a study analysis phase based on assessment via date and time. If time is not collected for a particular assessment, then assignment will be to the previous study analysis phase, i.e. to the screening phase for patients who directly enter the trial into the maintenance period, or to the re-induction phase for patients who directly enter the trial into the re-induction period.

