### **Overall Maintenance Treatment Period**

The overall maintenance treatment period applies to all patients taking at least one dose of maintenance treatment regardless of flare occurrence. This period will be considered to understand long-term efficacy and safety of spesolimab.

Table 6.1: 4 Flow chart of analysis phases for overall maintenance treatment period

Study analysis phase	Description	Start (included)	End (included)
Screening  phase	Screening	Earliest of (Date of informed consent, first screening procedure)	Date/time of injection of first maintenance study drug minus 1 minute
Maintenance treatment phase & Residual effects period	Maintenance on-treatment period	Date/time of injection of first maintenance study drug (Day 1 for maintenance)	Date of end of (infusion or injection) of last administered spesolimab + 112 days at 23:59
Follow-up  phase	Off-treatment period	Date of end of (infusion or injection) of last administered spesolimab + 113 days at 12:00 a.m.	Latest of: i) Date of End-of-Study visit; ii) last contact date on End of Study page at 23:59

Dates are defined individually per patient. If more than one date is associated with a specific visit, measurements associated with a specific date are assigned to a study analysis phase according to the rules specified in the table. An analysis phase will not extend beyond the start date of the following phase.

 The off-treatment period (i.e. Follow-up phase) only exists if the trial completion date is after the date of end of last injection or infusion + 112 days.

 The screening phase does not exist for re-induction treated patients who subsequently receive maintenance treatment.

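### SAP 7.8.1 step 3 has no last-contact term, so an event-free patient lost before the EOS visit adds up to 112 unobserved days to the denominator of the primary rate

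*SAP*

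**What the plan says.** The primary endpoint is the exposure-adjusted rate of patients with a TEAE up to week 336 of maintenance. SAP 7.8.1 defines it in steps.

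- Step 1 describes the denominator as the "total time of subjects at risk in that treatment group to contribute the event to the analysis".
- Step 2 ends a patient's time at the onset of the event.
- Step 3 covers patients without the event: "the time at risk will be censored at min (date of death, date of end of applicable treatment period per" Section 6.1, or the cut-off date at an interim).

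Section 6.1 supplies the period ends:

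- Overall maintenance (Table 6.1: 4): "Date of end of (infusion or injection) of last administered spesolimab + 112 days at 23:59". Post-flare (Table 6.1: 3) has the same rule.
- Pre-flare, without flare treatment (Table 6.1: 2): "Date of injection of last maintenance study drug + 112 days at 11:59 p.m".
- Re-induction, when maintenance does not follow (Table 6.1: 1): "Date of end of infusion of last re-induction study drug + 112 days at 11:59 pm".
- Disease flare period (Table 6.1: 5): flare infusion plus 98 days.

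The last contact date is used only to close the follow-up phase that comes afterwards, for example "last contact date on End of Study page at 23:59" in Table 6.1: 4.

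On data collection, Protocol 3.3.4.2 states that after consent withdrawal "no further information may be collected for the purpose of the trial". Under Protocol 5.2.6.2 there is no active AE monitoring after a patient's end of trial, and what is then reported goes on the SAE form and not on the CRF. Protocol 6.2.3.1 places the EOS visit 16 weeks after the last dose for patients who stop early.

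**The concern.** The 112-day tail is fully observed only if the patient stays in contact until EOS. If an event-free patient leaves earlier, step 3 still counts the rest of the tail as time at risk. An ordinary TEAE on those days would not reliably reach the database, so the days enter the denominator with no matching chance of entering the numerator. That does not fit step 1, which limits the denominator to time in which a patient could contribute the event.

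The error runs one way: unobserved time lowers the rate. In a single-arm safety trial no comparator carries the same bias to offset it. Patients who attend EOS are unaffected, and so are patients who already have the event, because their time stopped at onset.

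**Working it through.** **1. Length of the tail.** 16 weeks × 7 = 112 days, which reproduces the SAP figure. The flow chart gives EOS day 2466 − EOT day 2353 = 113 days, consistent to within a day. Maximum credit per event-free leaver: 112 / 365.25 = 0.307 subject-years, reached only if contact ends on the day of the last dose. If last contact is 28 days later, the credit is 84 / 365.25 = 0.230. In the disease flare period the ceiling is 98 / 365.25 = 0.268.

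**2. Does another rule cap it?** Section 6.1 says that a phase may not run past the start of the next one. The next phase starts at day +113, so this does not act as a contact cap.

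**3. Effect per patient.** Let T be observed time at risk, k the number of event-free patients with no contact after the last dose, and X = 0.307 × k. The relative fall in the rate is X / (T + X).

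- General scale: k = 2, T = 60 gives 0.613 / 60.613 = 1.0%.
- Illustration: N = 80 is the synopsis figure for maintenance. Assume a mean time at risk of 0.4 years, so T = 32, and 70 patients with a TEAE. The rate on observed time is 70 / 32 = 218.8 per 100 subject-years. Under step 3 it becomes:

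| k | T + X | Rate | Fall |
|---|---|---|---|
| 1 | 32.31 | 216.7 | 0.9% |
| 2 | 32.61 | 214.6 | 1.9% |
| 3 | 32.92 | 212.6 | 2.8% |

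**4. Range under assumed hazards.** The documents give none of these inputs. Take a constant event hazard h, a constant stopping hazard d among event-free patients, and a share q of stoppers with no contact after the last dose. X is then roughly q × d × 0.307 of T, so the fall passes 2% when q × d exceeds about 0.067 per year (0.0204 / 0.307). The full calculation also puts the observed tails of the other patients into T. For h = 2.5 per year it gives:

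| d per year | q | Fall |
|---|---|---|
| 0.15 | 0.25 | 1.1% |
| 0.3 | 0.25 | 2.1% |
| 0.7 | 0.25 | 4.6% |
| 0.7 | 0.50 | 9.1% |

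**5. Common against rare events.** With the same d = 0.7 and q = 0.25, the fall is 4.68% at h = 4 and 4.41% at h = 0.02, so frequency alone hardly matters. A simulation with early-heavy stopping (0.9 per year in year 1, then 0.25) and q = 0.25 gives:

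| Link between stopping and TEAEs | Any TEAE | Less common TEAE (h = 0.02–0.3) |
|---|---|---|
| None (any-TEAE h = 2–3) | 5.4–5.6% | 3.2–3.9% |
| 80% of premature stops come with a TEAE (any-TEAE h = 1–3) | 1.1–1.3% | 3.2–3.9% |

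The ordering depends on how stopping relates to TEAEs, which the documents do not quantify.

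**The case against.** **The effect may be negligible.** The analysis is descriptive. With about 70 patients having an event, the relative standard error is about 1/√70 = 12%, above every scenario shown here. The EOS visit is required, so few patients may be affected. This stands as a reason to grade the point minor. It does not remove a bias of known direction that one term would correct.

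**A reader might infer that the any-TEAE effect is under 2% and that rarer TEAEs are hit harder.** The argument is plausible: worsening of UC must be recorded as an AE (Protocol 5.2.6.2), and flares and AEs are reasons for stopping (3.3.4.1), so most leavers may already have a TEAE. But both conclusions come from assuming a low stopping hazard among event-free patients. Several grounds for stopping need no AE: refusing re-consent to the changed dosing interval (3.1), individual benefit-risk review after the interim results (1.4), no clinical remission within 48 weeks, and the patient's own wish (3.3.4.1). The documents support neither the 2% limit nor the ordering.

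**The cap may exist elsewhere.** SAP 7.8.1 refers to an internal AE guide that is not available. The log of Global Amendment 1 (Protocol 11.1) shows a superseded formula "censored at the minimum of (drug stop date + 112 days; last contact date; or, date of database snapshot if interim analysis performed"). A reader might infer a conflict with the SAP. It is not one: the text is superseded, and Protocol 7.3.4 as supplied contains no formula. It shows only that the term is usable. The point concerns step 3 as printed.

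**The tail is not wholly blind.** For patients who stop early and agree to further contact, deaths, related SAEs and related AESIs are still to be reported (Protocol 5.2.6.2). That softens the point for those event types and bears on the fix.

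**The ceiling rests on 112 days.** Protocol 7.3.4 gives a residual effect period of 16 days. With that value the ceiling would be 16 / 365.25 = 0.044 subject-years, and a patient last seen 28 days after the last dose would get no excess credit.

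**Conclusion.** The concern holds, as a minor one. As written, step 3 credits an event-free patient lost before EOS with up to 112 unobserved days and so understates the exposure-adjusted rate, including the primary endpoint. The missing term and the direction follow from the text. The size does not: it is at most about 1% per 2 such patients per 60 subject-years, small for any TEAE if most leavers already had one, and a few percent or more otherwise. All hazards and missed-EOS shares above are assumptions. No ordering between common and rare TEAEs is claimed. The 112-day ceiling holds under the SAP's residual effect period.

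**What to change.** Change step 3 to: min(date of death, last contact date on the End of Study page, end of applicable treatment period per Section 6.1, cut-off date if interim). Report the number of event-free patients censored at last contact, so that readers can judge the size directly.

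Leave the TEAE numerator definition unchanged. It may seem tidy to drop events with onset after last contact as well, but that would move deaths, related SAEs or related AESIs inside the residual effect period out of the rate. It would depart from the TEAE definition and could lower serious-event rates.

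Reconcile the 16-day (Protocol 7.3.4) and 112-day (SAP 6.1) residual effect periods separately.

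The cost is one term and one reported count. The SAP already uses this date to close the follow-up phase, so no new data are needed. The downside is that reported rates become slightly less favourable.
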